3.5 Investigators

The study will be conducted at up to 20 investigative sites located in the US.

The study will be conducted by investigators who are determined by the sponsor to be suitably qualified by training and experience to conduct this study in compliance with all applicable GCP and FDA federal regulations or local regulations. Sub-investigators will be identified on the Form FDA 1572.

3.6 Study Duration

[figure not shown]
3.6.1 Enrollment A

A diagram of the study duration for each subject participating in Enrollment A is presented in Figure 2.

During Enrollment A, the study duration for a subject who participates only in the Randomization Period of the study will be up to 31 days, which includes up to 1 day for screening (if screening procedures need to be initiated the day before treatment), 14 days for treatment, and 8 days of follow-up, including the visit window of up to 8 additional days after the scheduled day to complete the final Test of Cure Visit.

The study duration for each subject who participates in both the Randomization Period and Optional Open-label Extension will be up to approximately 48 days, which includes up to 31 days for the Randomization Period followed by up to 17 days for the Optional Open-label Extension (which includes a visit window of up to 3 additional days after the 14-day treatment to complete the final study visit). This study duration takes into account that the Day OLE1 procedures will occur while the subject is already onsite for the Test of Cure or Early Termination Visit for the Randomization Period.

Figure 2: Diagram of Study Duration for Enrollment A

[figure not shown]

3.6.2 Enrollment B

A diagram of the study duration for each subject participating in Enrollment B is presented in Figure 3.

In Enrollment B, the study duration for each subject will be up to 19 days, which includes up to 1 day for screening (if screening procedures need to be initiated the day before treatment), 14 days of treatment, and a 1-day final study visit after the 14-day treatment (which has a visit window of up to 3 additional days).

Figure 3: Diagram of Study Duration for Enrollment B

4 STUDY SUBJECTS

4.1 Enrollment A

4.1.1 Inclusion Criteria

In order to be eligible for Enrollment A, subjects must meet all of the following criteria:

1. Male or non-pregnant, non-lactating females
2. Diagnosis of uncomplicated otomycosis of the external ear only, in the ear(s) that will be treated with study drug, with a score for fungal elements of >0 in each ear to be treated with study drug (see Section 7.4 for definitions of the scores for each of the otomycosis signs and symptoms). Subjects must also have at least two of the following signs or symptoms of otomycosis in each ear to be treated with study drug: pruritus, >1; debris, >1; or aural fullness, >0
3. General good health as determined by medical examination and medical history, and who are free of clinically significant disease, including diabetes mellitus that is not well-controlled or that could interfere with the study

4. Females of childbearing potential must have had a negative urine pregnancy test at Screening/Baseline and must agree to use an effective method of contraception (as defined in Section 8.5) from Screening/Baseline up through the Test of Cure Visit (see Section 6). Females of childbearing potential include any female who has experienced menarche and who has not undergone successful surgical sterilization (hysterectomy, bilateral tubal ligation or bilateral oophorectomy) or is not postmenopausal (defined as amenorrhea >12 consecutive months). Females who are using oral, implanted, or injectable contraceptive hormones, an intrauterine device (IUD), barrier methods (diaphragm, condoms, spermicide) to prevent pregnancy, practicing abstinence or where partner is sterile (e.g., vasectomy), should be considered to be of childbearing potential
5. Subjects and/or their caregivers (as appropriate for the age of the subject) must have full legal capacity to volunteer
6. Subjects and/or their caregivers must have completed an appropriately administered institutional review board (IRB)-approved informed consent and assent (as applicable) prior to any study related procedures
7. Subjects and their caregivers (as applicable) must agree to comply with all requirements of the protocol
8. For subjects with only one ear meeting all study eligibility criteria, the subject will be eligible for the study, and the ear meeting all eligibility criteria will be treated with study drug and considered to be the study ear for the purposes of study evaluations. In case of bilateral otomycosis in which both ears meet all study eligibility criteria, the subject will be eligible for the study, both ears may be treated with study drug, and the worse ear will be considered to be the study ear for the purposes of study evaluations. If both ears meet study eligibility criteria and are determined by the investigator to have the same degree of infection at Screening/Baseline, the left ear will be considered to be the study ear for the purposes of study evaluations.

4.1.2 Exclusion Criteria

Subjects meeting any of the following criteria will not be eligible for Enrollment A:

1. Any other dermatoses or conditions of the ear that may interfere with the evaluation of otomycosis or with safety evaluations, including concomitant otic infections (including bacterial infection) other than otomycosis that require antimicrobial treatment, disease that has spread beyond the external ear(s), or pre-existing skin atrophy of the affected ear(s) that will be treated with study drug
2. Tympanostomy tube or perforated tympanic membrane in the ear(s) that will be treated with study drug
3. History of prior surgery directly affecting and compromising the external auditory canal and/or tympanic membrane of the ear(s) that will be treated with study drug, except for prior tympanostomy tube(s) that have already been removed and completely healed
4. Use, in the ear(s) that will be treated with study drug, of any topical medicated treatments for otomycosis within 14 days of study entry:

- Topical corticosteroids prescribed specifically for the treatment of otomycosis are prohibited to be used within 14 days of study entry; however, use of topical corticosteroids for any other reason (e.g., for bacterial otitis externa and/or for control of symptoms in the ear such as itching and/or pain) will not require a 14-day washout
 - Alcohol and/or peroxide are prohibited when prescribed/used by a health care provider specifically for the treatment of otomycosis within 14 days of study entry; however, use of these substances for other purposes (e.g., as a drying agent) will not require a 14-day washout
 - Use of boric acid for any reason is prohibited within 14 days of study entry
5. Use of any systemic antifungal therapy within 28 days of study entry, warfarin within 28 days of study entry, immunosuppressive or immune-stimulating drugs within 28 days of study entry, or systemic steroids within 3 months of study entry
 6. Fever of $\geq 100^{\circ}\text{F}$ at study entry
 7. Otomycosis that has been unresponsive to previous antifungal treatment
 8. Known hypersensitivity to any of the components in the test formulation
 9. Participation in another investigative trial within 28 days of study entry
 10. Participation in the sponsor's previous miconazole oil Study HD-MCZ-PHII-DRF062016 unless the subject was enrolled into either the vehicle or the 7-day miconazole oil group of that study.

4.2 Enrollment B

4.2.1 Inclusion Criteria

In order to be eligible for Enrollment B, subjects must meet all of the following criteria:

1. Male or non-pregnant, non-lactating females
2. Presence or absence of uncomplicated otomycosis of the external ear only, with otomycosis defined as the presence of any signs and/or symptoms consistent with a clinical diagnosis of otomycosis in the judgment of the investigator
3. General good health as determined by medical examination and medical history, and who are free of clinically significant disease, including diabetes mellitus that is not well-controlled or that could interfere with the study
4. Females of childbearing potential must have had a negative urine pregnancy test at Screening/Baseline and must agree to use an effective method of contraception (as defined in Section 8.5) from Screening/Baseline up through the final study visit. Females of childbearing potential include any female who has experienced menarche and who has not undergone successful surgical sterilization (hysterectomy, bilateral tubal ligation or bilateral oophorectomy) or is not postmenopausal (defined as amenorrhea >12 consecutive months). Females who are using oral, implanted, or injectable contraceptive hormones, an intrauterine device (IUD), barrier methods (diaphragm, condoms, spermicide) to prevent pregnancy,

practicing abstinence or where partner is sterile (e.g., vasectomy), should be considered to be of childbearing potential

5. Subjects and/or their caregivers (as appropriate for the age of the subject) must have full legal capacity to volunteer
6. Subjects and/or their caregivers must have completed an appropriately administered institutional review board (IRB)-approved informed consent and assent (as applicable) prior to any study related procedures
7. Subjects and their caregivers (as applicable) must agree to comply with all requirements of the protocol
8. For subjects with only one ear meeting all study eligibility criteria, the subject will be eligible for the study, and the ear meeting all eligibility criteria will be treated with study drug. In subjects who do not have otomycosis, treatment will be in the left ear if both ears are otherwise eligible. In subjects who have otomycosis, treatment will be in the ear(s) with otomycosis, provided the ear(s) meets all eligibility criteria. If both ears are judged by the investigator to have otomycosis and both meet all eligibility criteria, both ears may be treated.

4.2.2 Exclusion Criteria

Subjects meeting any of the following criteria will not be eligible for Enrollment B:

1. Any other dermatoses or conditions of the ear that may interfere with safety evaluations, including concomitant otic infections (including bacterial infection) other than otomycosis that require antimicrobial treatment, disease that has spread beyond the external ear(s), or pre-existing skin atrophy of the affected ear(s) that will be treated with study drug
2. Tympanostomy tube or perforated tympanic membrane in the ear(s) that will be treated with study drug
3. History of prior surgery directly affecting and compromising the external auditory canal and/or tympanic membrane of the ear(s) that will be treated with study drug, except for prior tympanostomy tube(s) that have already been removed and completely healed
4. Use of any systemic antifungal therapy or warfarin within 28 days of study entry
5. Fever of $\geq 100^{\circ}\text{F}$ at study entry
6. Known hypersensitivity to any of the components in the test formulation
7. Participation in another investigative trial within 28 days of study entry
8. Participation in the sponsor's previous miconazole oil Study HD-MCZ-PHII-DRF062016 unless the subject was enrolled into either the vehicle or the 7-day miconazole oil group of that study
9. Previous participation in Enrollment A of this study, unless the subject is known never to received active treatment (miconazole oil) during Enrollment A.

4.3 Subject Discontinuation

A subject MAY be withdrawn from the study (at the discretion of the investigator, sponsor, and/or IRB) prior to study completion for any of the following reasons, including, but not limited to:

- A serious adverse event (SAE) occurring during the course of the study which precludes continued follow-up
- Intercurrent illness which may, in the investigator's opinion, significantly affect study assessments
- Failure to follow required study procedures
- For subjects participating in Enrollment A, a negative fungal culture at Screening/Baseline (as assessed after at least 14 days of incubation by the clinical laboratory performing the fungal cultures)

A subject MUST be discontinued prior to the final study visit for any of the following reasons:

- Whenever the subject decides it is in his/her best interest to withdraw
- Whenever the investigator decides it is in the subject's best interest to be withdrawn

Prior to discontinuing a subject, every effort should be made to contact the subject, schedule a final study visit, and obtain as much follow-up data as possible. If possible, the assessment schedule for the Test of Cure Visit (Randomization Period) or the End of Treatment Visit (Optional Open-label Extension or Enrollment B) should be performed, and an effort should be made to collect all study drug. A fungal culture is not required for subjects who are prematurely discontinued from the study.

For Enrollment A, due to the time required to obtain fungal culture results from Screening/Baseline, subjects will be enrolled into the study based on a clinical diagnosis of otomycosis (including the visible presence of fungal elements at Screening/Baseline), without a requirement for a positive fungal culture. Subjects who end up with a negative Screening/Baseline fungal culture are not required to be discontinued from the study, but these subjects will not be included in the primary efficacy analysis. Because the sponsor's goal is to have at least 128 subjects in the MITT population (see Section 10.4.2), the total number of subjects enrolled into Enrollment A may be higher or lower than 220, depending on the percentage of subjects who are eligible to be included in the MITT population.

Subject discontinuations will be documented clearly on the applicable electronic case report form (eCRF). Subjects who discontinue from the study will not be replaced, but additional subjects may be enrolled and randomized into Enrollment A if it appears that the estimated number of subjects for Enrollment A (approximately 220) is insufficient to meet the sponsor's goal of having at least 128 subjects in the MITT population. After completion of Enrollment A, additional subjects (i.e., exceeding the 390 subjects total for the study) may be enrolled into Enrollment B if it appears that the estimated total number of study subjects is insufficient to achieve at least 300 subjects who have been exposed to miconazole oil for 14 days who are evaluable for safety.

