6 STUDY SCHEDULE

6.1 Enrollment A

6.1.1 Study Flow Chart

The study schedule for Enrollment A is presented in Table 3.

Table 3 Study Schedule: Enrollment A

Evaluations and Procedures:	Randomization Period				Optional OLE	
	Screen/ Baseline ^a Day 1	On Treat ^b Day 8	End of Treat ^b Day 15	Test of Cure ^c Day 22 ^d	Start of Treat Day OLE1 ^e	End of Treat Day OLE15 ^b
Informed consent/assent	X					
Inclusion/exclusion criteria	X					
Medical/medication history	X					
Physical examination	X					
Otomycosis signs and symptoms	X	X	X	X		X
Urine pregnancy test ^f	X			X		X
Randomization	X					
Dispensation of study drug	X				X	
Dispensation of subject diary	X				X	
Collection of subject diary		X ^g	X			X
Administration of study drug at site	X				X	
Weighing of study drug	X	X	X		X	X
Collection of study drug			X			X
Fungal culture ^h	X		X	X		
Ear cleaning	X	X				
AE evaluations	X	X	X	X	X	X
Concomitant medications review	X	X	X	X	X	X

- a. Procedures for this visit may occur over a 2-day period, if necessary (with Day 1 defined as the first day on which study drug is administered). All procedures for this visit must occur before the first administration of study drug with the exceptions that AE evaluations and review of concomitant medications will also occur after the start of study drug on Day 1.
- b. This visit may occur up to 3 days later than the specified day.
- c. This visit may occur up to 1 day sooner or up to 8 days later than the specified day.
- d. In case of early termination, the assessments planned for the Test of Cure Visit should be performed with the exception of fungal culture, which is not required.
- e. This visit will occur on the same day as the final visit of the Randomization Period.
- f. Females of childbearing potential only.
- g. The subject diary will be returned to the subject after review by study staff for documentation of missed and/or extra study drug doses.
- h. Samples will be used for growth and identification of fungal organisms as well as susceptibility testing to miconazole. Fungal cultures are not required to be taken at Day 15 or at Day 22 for subjects known to have a negative fungal culture at Screening/Baseline (assessed after at least 14 days of incubation by the clinical laboratory performing the fungal cultures).

OLE=Open-label Extension; Screen=Screening; Treat=Treatment

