10.4.3 Per Protocol Population

The per protocol (PP) population will be a subset of the MITT population and will include all subjects who complete the Test of Cure visit without any major protocol violations. The PP population will include subjects in the MITT population who did not meet any of the following criteria:

- Violated the inclusion/exclusion criteria
- Used an interfering concomitant medication
- Did not attend the Test of Cure visit
- Did not attend the End of Treatment visit
- Have not been compliant with the dosing regimen (i.e., subjects must have received 80%-120% of the expected applications of study medication in the study ear during participation in the study)
- Out of visit window at the Test of Cure Visit (-1/+8 days)

Subjects who discontinue from the study due to an adverse event related to study treatment, documented lack of treatment effect, or worsening of condition will be included in the PP population. Prior to breaking the blind, other additional criteria may be added to the list to accommodate for unforeseen events that occurred during the conduct of the trial that result in noteworthy study protocol violations.

All efficacy analyses will be performed using the PP population in a supportive manner.

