10.5.4 Missing Data

Missing data will be imputed as treatment failures for the primary and secondary efficacy analyses.

Missing data otherwise will not be imputed.

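### Section 4.3 does not separate stopping study drug from leaving the study, so MITT subjects who could be assessed at Day 22 may become imputed failures

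*Combined protocol and SAP*

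**What the plan says.** Section 4.3 (Subject Discontinuation) states: "A subject MAY be withdrawn from the study (at the discretion of the investigator, sponsor, and/or IRB) prior to study completion". Two of its listed reasons are "Failure to follow required study procedures" and "Intercurrent illness which may, in the investigator's opinion, significantly affect study assessments". The list is expressly non-exhaustive. The serious adverse event reason beside them is limited to events that rule out further follow-up; these two have no such limit.

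The same section asks that, before discontinuation, "every effort should be made to contact the subject, schedule a final study visit, and obtain as much follow-up data as possible", with the Test of Cure assessments done if possible. It then adds: "A fungal culture is not required for subjects who are prematurely discontinued from the study". Footnote d to Table 3 (section 6.1.1) says the same for early termination: "the assessments planned for the Test of Cure Visit should be performed with the exception of fungal culture, which is not required". Section 6.1.2.4 repeats the exception.

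Section 10.1.1 defines the primary endpoint, therapeutic cure, as a negative culture plus absence of all signs and symptoms at the Test of Cure Visit. Section 10.4.2 places every randomized subject with a positive baseline culture in the MITT population, with no adherence condition. Section 10.5.4 states: "Missing data will be imputed as treatment failures for the primary and secondary efficacy analyses". Non-adherence has its own place in section 10.4.3, where the per-protocol exclusions include subjects who "Have not been compliant with the dosing regimen".

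**The concern.** A subject who skips doses or catches an unrelated illness has not asked to leave and may be able to attend Day 22. If the trial withdraws that subject, the culture is no longer required, cure cannot be shown without it, and the subject stays in the MITT denominator as a failure. The missing outcome then results from a trial decision and not from the subject being unavailable.

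Two things are at stake. Imputing failures at the same rate in both arms shrinks the difference, because more cures are lost where cures are more frequent, and this costs power. If withdrawal differs by arm, part of the observed difference reflects who was withdrawn. Mycological cure, first in the gated secondary sequence of section 10.5.1.1, is exposed in the same way because it rests wholly on the waived culture.

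**Working it through.** **Inputs.** Section 10.3: 25.0% versus 7.1%, chi-square test, two-sided 0.05, 80% power, 128 MITT subjects (64 per arm), about 58% culture-positive among 220 enrolled. Section 9.2: 1:1 allocation. Section 4.3: discontinued subjects are not replaced. The proportion withdrawn for these two reasons, w, is not in the documents; 2% to 10% is an assumption.

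**Step 1: reproduce the plan's figure.** With d = p1 − p2 and p̄ the mean of the two rates,

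power = Φ{ [d√n − 1.96√(2p̄(1−p̄))] / √(p1(1−p1) + p2(1−p2)) }.

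For p1 = 0.25, p2 = 0.071 and n = 64: d√n = 1.432; 1.96√0.2695 = 1.017; the denominator is √0.2535 = 0.503. So Φ(0.823) = 79.5%. Solving for 80% gives 65 per arm, or 130 in total. Exact enumeration of the chi-square rejection region at 64 per arm gives 81.0%. The stated 128 reproduces.

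**Step 2: look for an allowance.** 220 × 0.58 = 127.6. The inflation from 128 to 220 covers culture positivity only and leaves nothing for missing Day 22 outcomes.

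**Step 3: equal withdrawal in both arms.** If a fraction w of each arm is imputed as failure and would otherwise have responded at the planning rates, each rate is multiplied by (1 − w).

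| w (assumed) | Miconazole | Vehicle | Difference (points) | Power, formula | Power, exact |
|---|---|---|---|---|---|
| 0% | 25.0% | 7.1% | 17.9 | 79.5% | 81.0% |
| 2% | 24.5% | 7.0% | 17.5 | 78.5% | 80.0% |
| 5% | 23.8% | 6.7% | 17.0 | 76.9% | 78.5% |
| 10% | 22.5% | 6.4% | 16.1 | 74.2% | 75.9% |

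In subjects, w = 2% is 64 × 0.02 = 1.3 per arm and 1.3 × 0.25 = 0.3 expected miconazole cures lost. At w = 10% it is 6.4 per arm and 1.6 cures.

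**Step 4: unequal withdrawal.** 10% withdrawn from miconazole and none from vehicle gives 0.225 versus 0.071 and 69.3% power. None from miconazole and 10% from vehicle gives 0.25 versus 0.0639 and 83.3%. With no true effect and a common cure rate of 7.1% or 25%, withdrawing 10% of vehicle only raises the exact chance of a significant result favouring miconazole from about 2.5% to 3.5% or 5.2%. With equal arm sizes, withdrawing miconazole only does the same in favour of vehicle.

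**Step 5: does other text close the gap?** The final-visit effort applies at the time of discontinuation, not at Day 22, and leaves the culture optional. The plan does not say whether early-termination data count as Test of Cure. The tipping-point analysis (section 10.5.5) explores missing primary outcomes but cannot recover them, and it does not cover the secondary endpoints. The per-protocol set is supportive and does not change the MITT outcome.

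**The case against.** The clause is permissive and may be used rarely. At 2% the loss is about one point, and exact power is still 80.0%. Section 4.4 lets subjects who miss a visit be scheduled for a later one and requires calls and a letter before loss to follow-up. Section 7.11 already has deviations documented. A culture at early termination is not required, but it is not forbidden either. Some who fail to follow procedures will be missing visits or refusing cultures, and their outcomes are lost under any wording. Subjects with remaining signs or symptoms fail therapeutic cure anyway, and non-adherent subjects may respond less than the planning rates. Withdrawal decisions are made blinded (section 9.3). Where illness distorts the Day 22 scores, counting the subject as a failure is a defensible strategy, and section 13.2 records that failure imputation followed an FDA comment.

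Most of this stands. It means the power figures lean towards overstating the loss. It does not justify discretion over which assessable subjects supply a primary outcome.

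A reader might go further in three ways that the documents do not support. One is to take the roughly 10% non-completion in section 3.4.2 as the withdrawal rate; that figure is 14-day treatment non-completion used for the exposure count. Another is to conclude that the clause favours miconazole; step 4 shows that it can act either way, and nothing indicates which arm would lose more subjects. A third is to call the sample size wrong; 128 reproduces on its own assumptions.

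**Conclusion.** The point holds as an avoidable source of missing primary outcomes. The route from discretionary withdrawal to imputed failure is open in the current text, and the mitigating provisions narrow it without closing it. Its size is unknown. The illustrated fall in formula power from 79.5% to between 78.5% and 74.2% (exact: 81.0% to between 80.0% and 75.9%) rests on three assumptions: 2% to 10% of each arm affected, responses at the full planning rates, and planning rates that do not already include such losses. The direction of any bias from unequal withdrawal is undetermined. The main reason to act is that the correction is cheap.

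**What to change.** In section 4.3, for the Randomization Period, state that non-adherence and intercurrent illness are recorded as deviations or events and are not in themselves grounds for ending follow-up. Say that this also applies under the list's non-exhaustive wording; deleting the two bullets alone would leave the same discretion in place. Subjects who remain willing and able attend the planned Test of Cure Visit with sign and symptom scores and fungal culture, and the observed outcome is used in MITT.

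Amend the culture waiver in section 4.3, Table 3 footnote d and section 6.1.2.4 so that it does not apply to these subjects unless their baseline culture is known to be negative. Without this, a subject kept in follow-up could still lack the required culture.

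Withdrawal by the subject, or in the subject's best interest, stays as written. Non-adherence is handled through the per-protocol set. No rule on stopping treatment changes.

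The cost is a wording change and a few already-scheduled Day 22 visits and cultures in non-adherent subjects. Some Day 22 scores may be affected by the intercurrent illness. No new procedure and no extra subjects are needed.
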